#### **5.4 Duration of Follow Up**

Patients will be followed according to the follow-up timepoints in Table 10-2. Patients who are in CR will be followed until clinical relapse (defined as loss of HR, development of disease related symptoms, or organomegaly), subsequent therapy, death, or withdrawal of consent. Patients in CR should not receive any anti-cancer therapies for remission maintenance. Patients removed from study for unacceptable AEs will be followed until resolution or stabilization of the AE. The sponsor may, in the future, request that subjects be transitioned to a long-term follow-up study to allow for closure of the study database and final reporting of the primary outcome, while allowing for additional follow-up under a separate study to facilitate assessment of secondary endpoints.

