### 3.3.4 Tests in Follow-up After Treatment Ends:

#### 3.3.4.1 All patients 28-42 days after the first day of dosing of prior cycle (end of treatment assessment)

- History and physical exam, concurrent medications, AEs, performance status (ECOG)
- Pulse Oximetry with vital signs and weight
- Ophthalmologic exam (slit lamp and fundus)
- 12-lead ECG (analyzed by central vendor, ERT)
- Imaging with CT or MRI for lymphadenopathy and organomegaly
- Bone marrow biopsy and aspirate with flow cytometry/sequencing
- CBC with differential (no peripheral blood smear)
- Chem 7 (sodium, potassium, chloride, bicarbonate, glucose, BUN, creatinine)
- mineral panel (calcium, magnesium, phosphorus, albumin)
- Hepatic panel (AST-SGPT, ALT-SGOT, total bilirubin, direct bilirubin, alkaline phosphatase)
- Uric acid, total protein, triglycerides, cholesterol, GGT
- PT, PTT, LDH, fibrinogen, quantitative immunoglobulins, CK, CRP, serum ferritin

- TSH, fT4, serum amylase, serum lipase, haptoglobin, and urinalysis
- [REDACTED]
- [REDACTED]
- [REDACTED]
- Patients with SD, PR or CR are then followed until relapse from baseline

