### **Relapse**

- Relapse from CR: Loss of criteria needed for CR, excluding transient decrease in lab values below criteria for CR.
- Relapse from PR: Loss of criteria needed for PR, excluding transient decrease in lab values below criteria for PR.
- Relapse from SD: Patients who meet above criteria for PD when compared to measurements after end of therapy.

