#### **13.4.1.1 CR Rate, Duration of CR (Disease-Free Survival), and Duration of Hematologic Remission**

The CR rate is defined as the proportion of subjects that have achieved CR. The 95% CI of the CR rate will be constructed using the exact probability method (Clopper-Pearson exact interval). Duration of CR (also called disease-free survival) will be measured from the first documentation of CR (by imaging, bone marrow biopsy and blood counts) to the time of relapse as defined in Section 11.1. Duration of HR will be measured from the first documentation of CR (by imaging, bone marrow biopsy and blood counts) to the time of loss of HR. Duration of CR will be censored on the date of the last disease assessment or clinical

response assessment for subjects who have no documented relapse prior to data cutoff, dropout, or the initiation of alternative anticancer therapy. Duration of HR will be censored on the date of the last evaluable hematologic assessment for subjects who have no documented loss of HR prior to data cutoff, dropout, or the initiation of alternative anticancer therapy. The proportion of subjects with a CR and HR at certain time points (eg, 6 month, 1 year, or 2 year) and the median duration of CR and HR may be estimated, if feasible, for the subgroup of subjects with CR using the Kaplan-Meier method. It should be noted that CR duration, which may be shorter than HR duration, is a secondary endpoint and will be summarized separately.

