### 13.5 Sample Size and Power Calculations

The sample size estimation in this study is based on the assumption that the historical durable CR rate in this population is  $\leq 13\%$  (null hypothesis). [REDACTED], a total of 77 subjects will provide 90% power to detect a difference between 28% and 13% durable CR rates at a 2-sided significance level of 0.05. [REDACTED]

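### Section 5.4 can end follow-up of CR patients on symptoms or organomegaly while hematologic remission is intact, in conflict with Sections 5.3, 5.5 and 11.1

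*Protocol*

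**What the plan says.** **End of follow-up.** Under Section 5.4, a patient in CR is "followed until clinical relapse (defined as loss of HR, development of disease related symptoms, or organomegaly"), or until subsequent therapy, death or withdrawal of consent. The three parts of clinical relapse are joined by an *or*, so any one is enough.

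**Relapse.** Section 11.1 gives "Relapse from CR: Loss of criteria needed for CR, excluding transient decrease in lab values below criteria for CR". The CR criteria there are leukemic cells in blood or marrow, organ and node size on CT or MRI, and blood counts. Symptoms are not listed under CR, PR, PD, SD or relapse.

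**Primary endpoint.** Sections 11.1 and 13.3 require CR, then HR for more than 180 days. HR means the blood counts needed for CR and nothing else. The rate is taken over all treated subjects.

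**Time-to-event endpoints.** Section 13.4.1.1 takes the end of CR from Section 11.1 and censors patients without a documented relapse. It censors duration of HR for those with "no documented loss of HR prior to data cutoff, dropout, or the initiation of alternative anticancer therapy". Section 13.4.1.5 censors PFS at the last hematologic assessment when there is no relapse, PD or death.

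**Other follow-up statements.** Section 5.3 keeps patients who are off drug on the Table 10-2 assessments, and symptoms are not among its exceptions. Section 5.5 takes a patient off study when progression or relapse is confirmed. Section 3.3.4.1 says "Patients with SD, PR or CR are then followed until relapse from baseline".

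**The concern.** The primary endpoint is deliberately narrower than relapse in general. Section 11.1 lets CR end on counts, imaging or marrow, but asks only that counts hold for the durable CR endpoint. Section 13.4.1.1 adds that CR may be shorter than HR. To know whether HR exceeded 180 days, the counts must be taken until they are lost or the period has passed. Section 5.4 allows them to stop earlier, for a reason that is not a loss of HR.

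Two things are at stake:

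- A true durable CR may go unproven because the counts were not collected.
- In the duration and PFS curves, a patient whose follow-up ended on suspected disease is treated as event-free at the last assessment. If the suspicion is often right, that censoring is informative and the curves are too favorable.

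The trigger is the investigator's judgment in a single-arm study. The central review works from images, slides and CBC reports, so a symptom judgment need not lead to a centrally recorded event.

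**Working it through.** **1. The triggers in 5.4 against the endpoint definitions.** This assumes that follow-up, including counts, stops at the trigger.

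| Trigger in 5.4 | Loss of HR? | Section 11.1 relapse from CR? | Duration of HR | Duration of CR and PFS |
|---|---|---|---|---|
| Loss of HR | yes | yes | event | event |
| Organomegaly shown on CT or MRI | no | yes | censored | event |
| Symptoms only | no | no | censored | censored |

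TTF is censored in the same way as PFS, unless alternate therapy is started and recorded, which is a TTF event. In the last two rows the primary endpoint cannot be confirmed if the trigger comes before HR has lasted more than 180 days. After that, only the censoring is affected.

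**2. The follow-up statements side by side.** The first sentence of 5.4 and Section 5.3 keep the symptom-only patient on Table 10-2. Section 5.5 removes a patient only for confirmed relapse, which symptoms alone are not. The specific sentence on CR patients in 5.4 ends follow-up. A site could follow either.

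Section 5.5 leaves a further gap. Relapse shown only on imaging or marrow is a confirmed Section 11.1 relapse, so it can take a patient off study while counts are still normal.

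**3. The plan's own figure.** Section 13.5 states that "a total of 77 subjects will provide 90% power". The comparison is of a 28% rate with a 13% rate, tested two-sided at 5%.

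- Inputs: n = 77, null rate 0.13, alternative 0.28, upper-tail error 0.025.
- Critical value: the smallest r with P(X ≥ r | 77, 0.13) ≤ 0.025 is 17 (tail 0.0189). At 16 the tail is 0.0375.
- Power: P(X ≥ 17 | 77, 0.28) = 0.903. The stated 90% is reproduced.
- Clopper-Pearson 95% lower limits: 13.4% for 17/77 and 12.4% for 16/77, against 13%.

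**4. Size per patient.** 1/77 = 0.013, or 1.3 percentage points.

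**5. Sensitivity.** The share f of true durable CRs lost because counts stopped early is not in the protocol, so it is assumed here, and each lost patient is counted as a non-responder. Expected durable CRs are 77 × 0.28 = 21.6. Rate = 0.28 × (1 − f); power = P(X ≥ 17 | 77, rate).

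| f (assumed) | Patients lost (21.6 × f) | Rate | Power |
|---|---|---|---|
| 0% | 0 | 28.0% | 90.3% |
| 2% | 0.4 | 27.4% | 88.3% |
| 5% | 1.1 | 26.6% | 84.8% |
| 10% | 2.2 | 25.2% | 77.4% |
| 20% (extreme) | 4.3 | 22.4% | 57.1% |

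**The case against.** The strongest reply is that this is loose wording with little practical effect. Sections 5.3 and 5.5 and the first sentence of 5.4 can all be read as keeping a symptom-only patient on schedule. Section 5.5.1 names only withdrawal of consent and loss to follow-up as reasons for not completing before Day 181. Section 2.2 ties HCL symptoms to splenomegaly and anemia, so disease-related symptoms with normal counts and no organomegaly should be rare. About 21 to 22 durable CRs are expected under the alternative and 17 are needed, so one lost patient seldom decides the result. The contrast between 16/77 and 17/77 holds for any patient in any single-arm trial.

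Much of this stands. It limits the frequency and shows that the literal reading of 5.4 is not the only one. It does not remove the conflict, because the sentence in 5.4 is the one written specifically for CR patients. The link between symptoms and splenomegaly also leads to the organomegaly trigger, which can stop counts with HR intact.

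Three stronger readings are tempting, and the documents do not support them:

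- *A reader might infer that such a patient definitely leaves and is a primary failure.* The visible text gives no rule for incomplete HR follow-up, part of 13.3 is redacted, and the SAP is not at hand. Counting the patient as a non-responder is the likely treatment, not a stated one.
- *A reader might call it contradictory to count a patient as a non-responder in the rate and censor the same patient in a survival curve.* That is ordinary practice for any dropout. The problem is the avoidable loss of data.
- *A reader might take the sensitivity table as a forecast of lost power.* Its shares are assumptions, and the stated 90% is correct.

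**Conclusion.** The point holds as an inconsistency that puts ascertainment of the primary endpoint at avoidable risk. The end-of-follow-up rule for CR patients contains one trigger that no endpoint recognizes (symptoms) and another that is not a loss of HR (organomegaly). It also conflicts with Sections 5.3 and 5.5 and with its own opening sentence.

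Each CR patient whose counts stop before HR has passed 180 days costs up to 1.3 points of the durable CR rate, if HR would have held and the patient is counted as a non-responder. The number of such patients is unknown and probably small. Later departures affect only the censoring of the secondary endpoints. The case for acting does not depend on the frequency: the analysis plan can set a censoring rule, but it cannot supply missing counts.

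The phrase in 3.3.4.1 is a minor matter. Section 11.1 measures relapse against the response criteria or, for SD, against measurements after therapy, and the endpoint definitions rely on 11.1. The phrase changes no endpoint.

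**What to change.** 1. In Section 5.4, replace the separate definition of clinical relapse with relapse as defined in Section 11.1, and reconcile the sentence with Sections 5.3 and 5.5.
2. Add to Section 5.4, with a matching exception in 5.5: *For every patient who achieves CR, the scheduled CBCs continue until loss of HR or the Day 181 count, and in any case for more than 180 days after first CR, whatever the symptoms, organomegaly or other evidence of relapse, unless consent is withdrawn, the patient dies or alternative therapy starts.* The first change alone is not enough, because relapse on imaging or marrow is a Section 11.1 relapse that can occur with HR intact.
3. In Section 3.3.4.1, refer to relapse as defined in Section 11.1 instead of relapse from baseline.

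No additional marrow or imaging examination is needed. Section 3.3.4.2 already schedules monthly CBCs to Day 181 for patients in CR. The cost is the wording changes and a few patients who continue scheduled counts a little longer.

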#### **5.5 Off Study Criteria**

- Unexpected illness or other comorbid condition, by PI discretion after consultation with the sponsor
- Manufacturer no longer able to supply study agent
- Participant requests to be withdrawn from study
- Patient has completed study intervention and follow-up period
- Death
- Subject non-compliance that, in the opinion of the investigator or sponsor, warrant withdrawal (eg, refusal to adhere to scheduled visits)
- Initiation of alternative anticancer therapy including another investigational agent
- Confirmation of disease progression or relapse
- Lost to follow-up

The reason for study removal and the date the patient was removed must be documented in the electronic case report form (eCRF).

### 5.5.1 Study Timetable and End of Study

An individual subject will be considered to have completed the study if the subject was followed through the Day 181 post-end of treatment visit, regardless of the number of doses of investigational product that was received. Subjects are encouraged to continue study follow-up detailed in [Table 10-2](#) so that duration of response to moxetumomab pasudotox can be determined.

Subjects will be considered not to have completed the study if consent was withdrawn or the subject was lost to follow-up if prior to completion of the Day 181 post-end of treatment visit.

The end of the study (“study completion”) is defined as the date of the last protocol-specified visit/assessment (including telephone contact) for the last subject in the study. This date will be 3 years after the final subject is entered into the study.

## 6 DOSING DELAYS/DOSE MODIFICATIONS

- There will be no dose reductions for moxetumomab pasudotox.
- Dosing may be delayed up to 2 weeks for toxicity or logistical reasons. Patients should not begin a subsequent treatment cycle of moxetumomab if there is active, ongoing infection requiring treatment. Patients with excessive delay (delay > 2 weeks) are permanently discontinued from treatment and should be followed but not retreated.
- Moxetumomab pasudotox infusion should be interrupted for Grade 2 or Grade 3 infusion related reactions (eg, rapid tumor lysis) and should be permanently discontinued for Grade 4 (life-threatening) anaphylaxis or hypersensitivity reaction
- Patients with  $\geq$  Grade 3 CLS or  $\geq$  Grade 3 HUS should be permanently discontinued from treatment.
- If the ANC is  $< 1.0 \times 10^9/L$ , dosing should be held during Grade 1 or higher fever ( $\geq 38.0^\circ C$ ).
- Dosing should be delayed until Grade 3 or Grade 4 AEs attributed to the study drug decrease to at least Grade 2 or below EXCEPT for the following (ie, dosing delay not required if any of the following are present):
  - Grade 3 hematologic toxicity.
  - Grade 4 hematologic toxicity resolving within < 4 weeks (lymphopenia, leukopenia and lymphocyte subsets will not be considered as grounds for a dosing delay).
  - Hematologic toxicity managed with transfusion and/or other support.
  - Grade 3 transaminase elevations.
  - Grade 3 electrolyte and mineral levels, hyperlipidemia, lipase, proteinuria and fever not associated with  $ANC < 1.0 \times 10^9/L$ .

- Hypocalcemia is graded after correction for the albumin, which increases the measured calcium level by 0.2 mmol/L or 0.8 mg/dL for each 1 g/dL of albumin less than 4 g/dL.
- An event of  $\geq$  Grade 2 hypercalcemia with calcium level corrected for serum albumin will require a delay in dosing until resolution to  $<$  Grade 2.
- Worsening of the coagulation profile of patients on anticoagulation.
- Grade 4 hyperlipidemia if pre-existing at Grade 2-4 levels or resolved to  $<$  Grade 4 by  $<$  2 months.
- Grade 3 hypoalbuminemia unless related to CLS.
- After dosing delays and re-challenge:
  - Patients who redevelop  $\geq$  Grade 3 non-hematologic toxicities, which are not covered by the exclusions in this section, with at least possible attribution to the study drug, will result in the patient discontinuing treatment but not off-study.

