### 3.1.2 Exclusion Criteria

1. Patients who have had chemotherapy, immunotherapy or radiotherapy within 4 weeks prior to initiation of treatment.
2. Patients who are receiving any other investigational agents.
3. Patients with known brain metastases should be excluded from this clinical trial because of their poor prognosis and because they often develop progressive neurologic dysfunction that would confound the evaluation of neurologic and other adverse events (AEs).
4. Patients with retinal or choroidal detachment identified during the screening ophthalmologic evaluation.

5. Pregnant or breastfeeding females. [REDACTED]
6. Positive for Hepatitis B core antibody or surface antigen unless the patient is on Lamivudine or Entecavir and Hepatitis B Viral deoxyribonucleic acid (DNA) load is < 2000 IU/mL.
7. Active second malignancy requiring treatment other than minor resection of indolent cancers like basal cell and squamous skin cancers.
8. Uncontrolled intercurrent illness including, but not limited to, ongoing or active infection, symptomatic congestive heart failure, unstable angina pectoris, uncontrolled hypertension, cardiac arrhythmia, malaria infection, or psychiatric illness/social situations that would limit compliance with study requirements.
9. Known human immunodeficiency virus (HIV)-positive patients unless taking appropriate anti-HIV medications with a CD4 count of > 200 [REDACTED]
10. History of allogeneic bone marrow transplant.
11. Patients with history of both thromboembolism and known congenital hypercoagulable conditions.
12. Uncontrolled pulmonary infection, pulmonary edema
13. Oxygen saturation at rest < 88% measured by pulse oximetry or PaO2 ≤ 55 mm Hg
14. Serum albumin < 2 g/dL
15. Radioimmunotherapy within 2 years prior to enrollment in the study.
16. Absolute neutrophil count (ANC) < 1.0 x 10^9/L, or platelet count < 50 x 10^9/L, unless judged by the investigator to be due to underlying disease (ie, potentially reversible with anti-neoplastic therapy). A patient will not be excluded because of pancytopenia ≥ Grade 3, or erythropoietin dependence, if due to disease, based on the results of bone marrow studies.

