#### **5.2.2.5 Hemolytic Uremic Syndrome**

Any subject with suspected Grade 1-4 HUS will be evaluated as for CLS and in addition will be followed with serial haptoglobin, LDH, CBCs, and urinalyses to detect urine free hemoglobin. Subjects with an unexplained drop in hemoglobin  $\geq 1.5$  g/dL during any treatment cycle should be evaluated for possible HUS. Peripheral blood will be assessed for schistocytes. Patients need not be managed with plasmapheresis, and rather may be managed with fluid repletion and/or diuretics at the discretion of the institution PI, with consultation of the sponsor. If HUS of any grade develops, treatment should be suspended until resolution of all laboratory abnormalities, and should only be resumed if the maximum grade was  $\leq 2$ , and after consultation and agreement with the sponsor. [REDACTED]

[REDACTED] Diuresis early on may worsen the creatinine by causing dehydration, and should only be used to treat symptoms of fluid overload. Patients may have creatinine elevations and/or microscopic hematuria without evidence of HUS, but such patients may be managed similarly with attention to adequate hydration. Patients should be observed carefully for evidence of severe HUS, including mental status abnormalities, renal failure, and bleeding from severe thrombocytopenia.

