#### **5.2.2.6 Ocular Events**

In the event of visual symptoms of Grade 2 or greater, an ophthalmologic evaluation is required. Subjects must be queried for and encouraged to report any ocular symptoms on dosing days prior to the administration of moxetumomab. [REDACTED]

[REDACTED] Due to the potential association of HUS with retinal damage, subjects with visual symptoms and new finding(s) on ophthalmologic examination should be

hospitalized with daily monitoring of renal function with serum creatinine and close observation.

If the subject displays any retinal abnormalities, dosing with the investigational agent must be discontinued. In the event that an ocular event or symptom occurs without any evidence of retinal abnormalities, dosing must be interrupted and may not resume until there is full resolution of ocular symptoms.

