### 5.3 Duration of Therapy

Treatment may continue until one of the following criteria applies:

- Completion of 6 cycles of therapy.
- Disease progression
- Documented CR without assessable MRD
- Treatment delay of > 2 weeks beyond scheduled start of subsequent cycle
- Intercurrent illness that prevents further administration of treatment
- Unacceptable AEs as defined in Section 6
- General or specific changes in the patient's condition render the patient unacceptable for further treatment in the judgment of the investigator.
- Severe or life-threatening anaphylaxis or hypersensitivity reaction
- Withdrawal of consent from further treatment with investigational product or lost to follow-up
- Subject is determined to have met one or more of the exclusion criteria or failed to meet all of the inclusion criteria for study participation
- Pregnancy
- Any of the following liver function abnormalities:
  - ALT or AST > 5 x ULN for more than 2 weeks
  - ALT or AST > 3 x ULN and (total bilirubin > 2 x ULN or INR > 1.5); see Section 7.6.2 for additional details regarding reporting of subjects with ALT or AST > 3 x ULN and total bilirubin > 2 x ULN with unknown etiology (ie, Hy's law cases)
  - ALT or AST > 3 x ULN with the appearance of fatigue, nausea, vomiting, right upper quadrant pain or tenderness, fever, rash, and/or eosinophilia (> 5%)
  - Corrected QT interval (Fridericia) > 500 msec confirmed (persistent for at least 5 minutes; based on manual over-read by medically qualified person) and determined post dose either during continuous 12-lead ECG monitoring or on a repeat 12-lead ECG

Subjects who are permanently discontinued from receiving investigational product will be followed for protocol-specified assessments (Table 10-2) including follow-up of any AEs unless consent is withdrawn specifically from further study participation, the subject is lost to follow-up, the subject starts alternative treatment, or the subject is enrolled in another clinical study.

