### 7.3.3 Ocular Events

Ocular events of special interest to the sponsor are defined as any clinically significant change in vision, retinal abnormalities, or choroidal disturbance that occurs during the course of the study. Subjects will be queried for ocular symptoms at screening, prior to initiation of a new treatment cycle, prior to administration of each moxetumomab dose, and at the end of treatment.

In the event of visual symptoms  $\geq$  Grade 2, ophthalmologic evaluation is required. If a subject has an ocular event with new abnormality by ophthalmologic examination during study treatment, PK and immunogenicity samples, and serum complement factors and serum Ig levels will be collected within 24 hours of diagnosis, during the event as clinically indicated (eg, in order to capture peak intensity of event as well as at least one time point during period of improvement), and after resolution of the event.

Due to the potential association of HUS with retinal damage, subjects should be hospitalized with daily monitoring of renal function with serum creatinine and close observation. If the subject displays any retinal abnormalities, dosing with the investigational agent must be permanently discontinued.

In the event of an ocular event or symptoms occur without any evidence of retinal abnormalities, dosing must be interrupted and may not resume until there is full resolution of ocular symptoms.

In the event of an ocular event where the etiology is unknown, timely follow-up investigations and inquiries must be initiated by the investigational site, based on medical judgment, to make an informed decision regarding the etiology of the event. Ocular events will be followed to resolution until the end of subject participation in the study. Prompt notification of the sponsor is required as with other AESIs.

[REDACTED]

Instructions to the site on how to record (in the eCRF) and report these events (to MedImmune Patient Safety) are provided in Section 7.4.3 and Section 7.6.4, respectively.

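### Section 6, where sites are sent for dosing delays and stops, does not match the HUS and ocular rules given elsewhere, and no order of precedence is stated

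*Protocol*

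**What the plan says.** Section 5.1 refers to Section 6 for dose modifications, and Section 5.1.1 refers to it for a dosing delay. Section 5.3 lists, among the reasons treatment ends, "Unacceptable AEs as defined in Section 6".

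Section 6 gives a general rule: "Dosing should be delayed until Grade 3 or Grade 4 AEs attributed to the study drug decrease to at least Grade 2 or below", followed by a list of exceptions. On HUS it has one bullet, set at Grade 3 or higher: "Grade 3 HUS should be permanently discontinued from treatment". It has no bullet on ocular events. A delay of more than 2 weeks means permanent discontinuation of treatment.

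The event-specific sections say more:

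- Section 5.2.2.5 on HUS: "If HUS of any grade develops, treatment should be suspended until resolution of all laboratory abnormalities". Treatment may resume only if the maximum grade was 2 or lower and the sponsor agrees.
- Section 5.2.2.6 on ocular events: "If the subject displays any retinal abnormalities, dosing with the investigational agent must be discontinued". Where there is an ocular event or symptom but no retinal abnormality, "dosing must be interrupted and may not resume until there is full resolution of ocular symptoms". No grade is attached to either rule.
- Section 7.3.3 repeats both ocular rules, but says the discontinuation is permanent.

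**The concern.** A site deciding whether to give the next dose will open Section 6, because three other sections direct it there. For HUS and ocular events, Section 6 is either silent or sets a lower bar for resuming than the section written for that event. It contains no reference to 5.2.2.5, 5.2.2.6 or 7.3.3, and no passage ranks the sections.

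The first stake is safety: a site working from Section 6 alone could redose during an adverse event of special interest when another section says to wait or stop. The second is consistency of conduct across sites in a single-arm multicenter trial. Because a delay beyond 2 weeks ends treatment, the choice between resuming at Grade 2 and waiting for full resolution can decide whether a patient receives the remaining cycles. Cycles received and the rate of discontinuation for adverse events could then depend partly on which section was consulted.

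**Working it through.** No figure in the protocol is in dispute, so the check sets the passages side by side, case by case.

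| Case | Section 6 (and 5.3) | Event-specific section | Result |
|---|---|---|---|
| HUS, Grade 3 or higher | Permanent stop | 5.2.2.5: suspend; no resumption above Grade 2 | Agree |
| HUS, Grade 1-2 | HUS bullet and general rule both start at Grade 3, so no hold is stated | 5.2.2.5: suspend until all laboratory abnormalities resolve; sponsor agreement to resume | Hold missing from Section 6 |
| Ocular event, Grade 3-4, drug-attributed, no retinal finding | General rule: may resume at Grade 2 | 5.2.2.6 and 7.3.3: resume only on full resolution of symptoms | Different thresholds for resuming |
| Ocular symptom, Grade 1-2, no retinal finding | No hold stated | 5.2.2.6 and 7.3.3: interrupt until full resolution | Hold missing from Section 6 |
| Retinal abnormality arising on study | No rule in 5.3 or Section 6 | 5.2.2.6: discontinue; 7.3.3: discontinue permanently | Stop missing; two wordings |

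Four further checks:

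1. Is Grade 1-2 HUS a real category here? Yes. Section 7.3.2 defines HUS Grades 1 to 4, so the any-grade rule in 5.2.2.5 covers events that Section 6 does not mention.
2. Does Section 6 ever act below Grade 3? Yes, for three named events: infusion-related reactions from Grade 2, albumin-corrected hypercalcemia from Grade 2, and fever from Grade 1 when the neutrophil count is below 1.0 x 10^9/L. It would therefore be wrong to say that Section 6 generally ignores Grade 1-2 events. These entries do show that the drafters place special holds in Section 6. The hypercalcemia hold stands both there and in 5.1.1; the HUS and ocular holds were not carried over.
3. Do the two ocular sections match each other? Not fully. Section 5.2.2.6 discontinues, while 7.3.3 discontinues permanently. Section 5.2.2.6 ties hospitalization to visual symptoms together with new examination findings. Section 7.3.3 states it in a sentence without that condition: "Due to the potential association of HUS with retinal damage, subjects should be hospitalized with daily monitoring of renal function".
4. Is the gap a product of redaction? Text is blacked out in 5.2.2.5, 5.2.2.6, 7.3.2 and 7.3.3, and qualifiers may be there. Sections 5.3 and 6 show no redaction, so the omissions from those two sections can be read in full.

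**The case against.** The best defense is that the sections complement each other. Section 6 stops HUS at Grade 3 or higher; 5.2.2.5 suspends lower grades and lets them resume with sponsor agreement. A site that reads both can obey both. The 5.3 reference concerns ending treatment, so it does not make Section 6 the only source of temporary holds. HUS and ocular events must reach the sponsor within 24 hours even when non-serious (Section 7.6.4), and visual symptoms are queried before each dose.

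Much of this stands. A reader might infer that Section 6 permits dosing in Grade 1-2 HUS, so that the sections give opposite instructions. The text does not go that far: Section 6 is silent, and silence is not permission. That case is an omission.

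A reader might also infer that the retinal stop reaches findings already present at screening, because eligibility excludes only "Patients with retinal or choroidal detachment identified during the screening ophthalmologic evaluation" and the stop sentence does not say the finding must be new. The documents do not support this as the rule. Section 7.3.3 defines ocular events of special interest as those occurring during the study, and in 5.2.2.6 the stop follows directly on a sentence about new findings. The point merits a clarifying phrase, but no count of wrongly stopped patients can be derived: the protocol gives neither the prevalence of baseline retinal findings nor the frequency of visual symptoms.

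The requirement for an eye examination from Grade 2 is a minimum and does not forbid one at Grade 1, so it is not counted here. The hospitalization difference is softened because the preceding paragraph in 7.3.3 concerns new abnormalities on examination.

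The defense does not remove the two resumption thresholds for a Grade 3-4 ocular event, or the absence of the retinal stop and the any-grade HUS suspension from Section 6. That the specific rule overrides the general one is a sensible reading, but no passage says so. Section 5.1.1 also refers dosing delays, not just stops, to Section 6. Rapid reporting limits the risk, but 7.6.4 sets no dosing hold.

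**Conclusion.** The point holds in a limited form. There is one direct mismatch (when dosing may resume after a drug-attributed Grade 3-4 ocular event without retinal findings) and two kinds of omission from the section that sites are told to use: the HUS and ocular holds below Grade 3, and the retinal stop, which is also absent from 5.3. The wording of 5.2.2.6 and 7.3.3 also differs on permanence and on hospitalization.

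The size cannot be put in numbers, because the document as shown gives no rates for these events by grade. An effect on the durable CR rate is possible through cycles lost or given, but it is not shown. The conclusion assumes that the redacted text in the HUS and ocular sections does not already state precedence. This is a drafting fault that should be corrected because it bears on dosing during adverse events of special interest. It does not undermine the design or the primary analysis.

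**What to change.** Reconcile Sections 5.3, 6, 5.2.2.5, 5.2.2.6 and 7.3.3 in one wording amendment:

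- Either carry the HUS and ocular hold and stop rules into Section 6, or state in Section 6 that the event-specific sections take precedence and name them.
- Make the reference in 5.3 cover the retinal stop.
- Make the ocular text in 5.2.2.6 and 7.3.3 identical, including whether discontinuation is permanent and the condition for hospitalization.
- As a lesser clarification, state whether a retinal abnormality is judged against the screening examination.

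Which grade, threshold or stopping rule applies is for the sponsor to decide; the requirement is only that the sections agree. The cost is a text amendment and notice to sites. No new assessment is needed, since the slit-lamp and fundus examination is already done at screening.
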